7.3 LOST TO FOLLOW-UP

A participant will be considered lost to follow-up if he or she fails to return for 2 scheduled visits and is unable to be contacted by the study site staff.

The following actions must be taken if a participant fails to return to the clinic for a required study visit:

- The site will attempt to contact the participant and reschedule the missed visit and counsel the participant on the importance of maintaining the assigned visit schedule and ascertain if the participant wishes to and/or should continue in the study.
- Before a participant is deemed lost to follow-up, the investigator or designee will make every effort to regain contact with the participant (where possible, 3 telephone calls and, if necessary, a certified

letter to the participant's last known mailing address or local equivalent methods). These contact attempts should be documented in the participant's medical record or study file.

- Should the participant continue to be unreachable, he or she will be considered to have withdrawn from the study with a primary reason of lost to follow-up.

8 STUDY ASSESSMENTS AND PROCEDURES

8.1 SCREENING

The site begins the screening process by obtaining informed consent from the patient. The site must ensure they are using the correct IRB approved version of the informed consent and are following their informed consent process. After obtaining informed consent for the patient, the site records the informed consent date in the Electronic Data Capture System (EDC), and then completes the inclusion/exclusion CRF page (this might also involve a serum pregnancy test if the subject is a female of childbearing potential). The site then submits the patient's CTA to the Core Lab, which can be done either electronically, or via mail. The site may now enter the Demographics & Vascular Characteristics (including vitals and serum creatinine) and Medical History information into the EDC.

The Core Lab reviews the CTA for anatomical inclusion/exclusion criteria conformity. If the subject does not pass this step the subject is dropped from further consideration. If the subject passes Core Lab, the subject is referred to the Case Review Board (CRB) for further evaluation.

The CRB reviews the case for overall trial suitability. The CRB may also make procedural recommendations to the Site. If the CRB recommends the subject for the study, the subject is approved for implantation.

Reasons for subject exclusions (Core Lab or CRB), along with any CRB procedural recommendations, will be captured and reported.

8.2 CASE REVIEW BOARD (CRB)

The Case Review Board consists of clinicians in the fields of vascular disease or radiology that have experience in the treatment of subjects with abdominal aortic aneurysm (AAA) and experience with the Nellix device. The CRB will evaluate clinical and anatomical criteria of each subject, as appropriate, and give advice regarding technical aspects of the procedure. The CRB may also recommend/require procedural steps.

8.3 SCHEDULE OF ACTIVITIES

Implantation

The subject is enrolled into the study upon the first attempt to insert the Nellix catheter into the patient. The subject is treated with the ChEVAS System, following the IFU. Procedural data is collected, including concomitant procedures, and device accountability information.

Discharge

Upon discharge of the subject from the hospital, ward stay information is collected, along with creatinine levels, blood pressure, and medications.

Follow-up visits (30 days, 6 months, 1 year, 2 years, 3 years, 4 years, and 5 years)

The site will schedule and conduct a clinical visit with each subject within the required follow-up visit windows (**Table 4**), where vitals will be collected. Required imaging and labs must also be conducted during the required visit window. The required imaging and labs include:

- CT with contrast (CTA), 3mm slice thickness maximum
 - Note: In cases of renal insufficiency, CT without contrast (3mm slice thickness maximum) and a duplex ultrasound may be conducted instead of the CTA
- X-ray (30-day, 1 year, 3 year and 5 year): 2-view abdominal (left and right oblique)
- Serum Creatinine

In addition to imaging, at each follow-up visit, medication categories will be collected, along with Adverse Event collection and assessment

The following table (**Table 4**) shows the required visit schedule. Subjects must have their required scans, visits, and labs completed within the given time frames.

TABLE 4 : VISIT WINDOW SCHEDULE

Visit	Beginning of visit window	Target Day	End of Visit Window
1 Month	16	30	44
6 Month	150	180	210
1 Year	305	365	425
2 Years	640	730	820
3 Years	1005	1095	1185
4 Years	1370	1460	1550
5 Years	1735	1825	1915

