1.2 SCHEMA

A schema is provided below, with further detail provided in Section 8.

Screening (Site)

- Obtain informed consent.
- Site screens potential participants by inclusion and exclusion criteria.
- Qualified CTA submitted to the Core Lab.

Screening (Core Lab)

- Core Lab reviews the CTA for anatomical inclusion/exclusion criteria conformity. If the subject does not pass this step the subject is dropped from further consideration.
- If the subject passes Core Lab, the subject is referred to the Case Review Board (CRB) for further evaluation.

Screening (CRB)

- The Case Review Board (CRB) reviews case for overall study suitability. The CRB may also make procedural recommendations to the Site.
- If the CRB recommends the subject for the study, the subject is approved for implantation. Baseline and Medical History data are entered by the site.

Enrollment

- The subject is enrolled into the study upon the first attempt to insert one of the ChEVAS System catheters into the patient.
- The subject is treated with the ChEVAS System.
- Procedural data are collected.

Discharge

- Ward stay information collected.
- Vitals and creatinine lab results collected.
- Medications and Adverse Event records.

1 Month, 6 Months, Annually

- CTA and X-rays are submitted to Core Lab.
- Vitals and creatinine lab results collected.
- Medications and Adverse Event records.

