exclusion while maintaining patency of the visceral arteries. The chimney stents are positioned first. Once the chimney stents are in position, the Nellix System EndoBags are introduced. The Nellix System is positioned so as the Nellix stents align with the top of the parallel stents and are aligned proximally to the planned sealing zone.^{96,97} Intraoperative angiography is used to confirm stent position. The chimney stents are deployed, and the chimney delivery systems are exchanged for PTA balloons. Some investigators prefer to use balloon expandable stents, as the balloons can be left in place during polymer curing, thereby protecting the chimney stents.^{94,96} The Nellix EndoBags are then filled with saline solution and intraoperative angiography is performed to confirm the absence of endoleaks. The saline is then removed from the EndoBags and they are filled with a polymer up under pressure monitoring. The polymer conforms around the branch stents and aortic vessel wall, thereby creating a seal to exclude blood flow to the aneurysm sac. The Nellix stents form lumens through which blood flows to the distal limbs and vasculature and the branch stents maintain blood flow to the visceral arteries. The EndoBags with cured polymer exclude the aneurysm from blood flow, preventing aneurysm pressurization and rupture. This seals the entire anatomy from the proximal end of target landing zone to the iliac arteries with a distal seal zone (**Figure 7**). To assess the technical success of the procedure, intraoperative angiography is performed to confirm exclusion of the aneurysm and to assess for endoleaks.

[figure not shown]

FIGURE 7: NELLIX SYSTEM WITH BRANCH STENTS IN A 3-VESSEL REPAIR

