A subject is enrolled into the trial at the point where one of the ChEVAS System catheters is inserted into the subject. All enrolled ChEVAS subjects will undergo the endovascular aneurysm repair procedure with the Nellix System, Verta stent grafts, and Ovation iX iliac limb extensions when needed. Subjects will be followed procedurally to discharge, at 30 days (primary 30-day endpoint), six months, one year (primary 1-year endpoint), and annually thereafter to five years (total follow-up commitment). These are the required follow-up imaging and visits of the study, though all subjects should be monitored and evaluated per instructions for use, standardized protocols, and institutional standards of care for patients who receive an endovascular stent graft, as long as the required follow-up (imaging and visits) within this protocol are followed.

The Primary analysis will be conducted on the implanted population within the ChEVAS Roll-In and Pivotal cohorts. A subpopulation is the per-protocol population, consisting of subjects that have an implanted device, and have not violated the anatomical or procedural IFU criteria. Standardized training and baseline imaging review should prevent the enrollment of subjects who would be considered off protocol. The primary 1-year (i.e. late) endpoint requires evaluable subjects, so completed cases (subjects who have enough information to be evaluated at 1 year) comprise an additional way to stratify the population. ChEVAS Roll-In subjects may be evaluated as a separate group for investigational purposes. The analysis is only meant to provide information as to the presence and extent of a learning curve and makes no impact to the method that will be utilized to evaluate the primary study endpoints. Subjects who initially consent but then withdraw prior to the procedure will not be included in any analysis.

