5.3 SCREEN FAILURES

Candidates who are consented to the trial, meet inclusion criteria, and do not meet any exclusion criteria will be considered a potential study subject. Subjects may be screen failed from the trial for any reason during the screening process. A subject is not considered enrolled until a ChEVAS System catheter is inserted in the subject. Once enrolled, subjects will be followed according to this protocol. The reasons for screen failures and all study exits must be reported on the case report form.

¹⁴ Landing zone is defined as the segment of a visceral vessel to be stented that does not include a significant branch artery

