7 STUDY INTERVENTION DISCONTINUATION AND PARTICIPANT DISCONTINUATION/WITHDRAWAL

7.1 DISCONTINUATION OF STUDY INTERVENTION

If an attempt is made to insert one of the ChEVAS System catheters into the subject, the subject is considered enrolled. If the procedure is aborted subsequent to the attempted insertion, the case will be considered a technical failure. The subject will be exited from the study after having completed 30 days of follow-up and recording of all adverse events up until 30 days. A 30-day CT on such a subject is not required.

If a subject is Converted to Open Repair at any time during the study, the subject will be exited from the study after 30 days of follow-up post-surgery.

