8.4 SAFETY AND OTHER ASSESSMENTS

Information collected at the following procedures/evaluations, as applicable:

- **Physical examination** Including weight, blood pressure, medication assessment. If patient exhibits potential neurological change, the patient will undergo an mRS exam for endpoint analysis
- **Blood Laboratory Analysis** Including Serum Creatinine, eGFR (calculated)
- **Contrast-enhanced CT scan:** imaging requirements include slice thickness of $\leq 3\text{mm}$; axial, coronary, sagittal views. To ensure consistency, below are the requirements for CT acquisition:
 - Only high resolution, contrast-enhanced spiral CT scans are acceptable. Sites are required to use radiation reduction techniques
 - Data must be uncompressed
 - **Preferred maximum slice spacing is 2mm.** In no case should it exceed 3mm
 - The preferred protocol, shown below, is easier to attain with a multi-row scanner. If the preferred protocol cannot be used, an alternate protocol is provided.
 - Instruct patient not to move during scan. Do not move table height, position, or field of view during scan. If such movement occurs, repeat scan in its entirety.

Parameter	Preferred	Alternate
Scan Mode	Helical/Spiral	
Scan Parameters	140kVp, Auto mA, 0.5sec	140kVp, 280mA (min), 1.0sec
Collimation	0.625 to 2mm	3mm
Slice Spacing	0.625 to 2mm	3mm
Superior Extent	Cervical Spine – C2 or base of ears	
Inferior Extent	Lesser trochanter of femur	
Patient Instruction	Single breath hold	1 st hold: above celiac to bifurcation 2 nd hold: bifurcation to lesser trochanter
Contrast*	Standard non-ionic	
Volume and Rate	150mL at 3 to 4 mL/sec or as per institutional standards	
Scan Delay	ROI - threshold 90Hu in aorta	
Field of View	Large body	
Window Level	400/40	

*For those subjects with renal insufficiency, a non-contrast CT and duplex ultrasound will be acceptable.

- **Procedural Information:** The Index Procedure CRF will capture all relevant procedural data including access times and types, anesthesia type, all devices implanted, any adjunctive devices used, timing of procedural events, post-procedural findings, complications and concomitant procedures performed, blood loss, contrast volume, fluoroscopy time and any observations on the procedure
- **Adverse Events:** these will be captured at any point after enrollment until study exit. This is determined by the time the patient enters the operating room or catheter lab.

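### The protocol gives three incompatible enrolment points, so the same aborted procedure can be an enrolled 1-month technical failure or not enrolled at all

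*Combined protocol and SAP*

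**What the plan says.** The current text defines enrolment in five places, in three different ways.

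- **Attempt with any ChEVAS System catheter.** Section 1.2: "The subject is enrolled into the study upon the first attempt to insert one of the ChEVAS System catheters into the patient". Section 7.1: "If an attempt is made to insert one of the ChEVAS System catheters into the subject, the subject is considered enrolled". Section 7.1 adds that a procedure aborted after that attempt is a technical failure, followed for 30 days.
- **Any ChEVAS System catheter inserted.** Section 4.1: "A subject is enrolled into the trial at the point where one of the ChEVAS System catheters is inserted into the subject". Section 5.3, on screen failures: "A subject is not considered enrolled until a ChEVAS System catheter is inserted in the subject".
- **Attempt with the Nellix catheter.** Section 8.3: "The subject is enrolled into the study upon the first attempt to insert the Nellix catheter into the patient".

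Section 8.4 collects adverse events from enrolment onwards and then says of the timing: "This is determined by the time the patient enters the operating room or catheter lab".

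Four other provisions matter:

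- Section 6.1.1 lists the Verta branch stent graft system as part of the ChEVAS System.
- Section 2.3.4 gives the order of the procedure: "The chimney stents are positioned first", and then "Once the chimney stents are in position, the Nellix System EndoBags are introduced".
- Section 3.1 makes technical failure a component of the 1-month primary endpoint and makes access and delivery of every component part of technical success.
- Sections 4.1 and 9.3 confine the primary analysis to implanted subjects, while Section 9.2 says all 120 subjects are analysed at 1 month.

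**The concern.** The three rules differ at the stage of the procedure where access and delivery failures happen. Under a narrower rule, such a failure leaves both the numerator and the denominator of the 1-month rate. Recruitment then continues until 120 subjects are enrolled, so the lost case is replaced by a patient who got past that stage. The error can run only one way, towards a lower event rate and an easier pass against 25%.

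Patient follow-up is also affected. Section 7.1 gives an aborted enrolled case 30 days of follow-up and adverse-event recording. A patient who is not enrolled has no clear claim to either. If the classification is left to be argued after the event, it will be decided with the outcome known.

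**Working it through.** **1. Two cases read against each rule**

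| Case | 1.2 and 7.1 | 4.1 and 5.3 | 8.3 |
|---|---|---|---|
| First ChEVAS catheter tried but cannot be introduced | Enrolled; technical failure if aborted | Not enrolled | Enrolled only if it is the Nellix catheter |
| Stopped after Verta insertion, before any Nellix attempt | Enrolled; technical failure | Enrolled | Not enrolled |

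The first case splits attempt from insertion. In the second, Section 8.3 alone disagrees. That case arises because Section 2.3.4 places the chimney stents before Nellix.

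**2. The plan's own figure**

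Inputs from Sections 9.1 and 9.2: n=120, goal 25%, expected rate 14.5%, exact binomial test, alpha 0.05. The sample-size text does not say whether alpha is one-sided; the hypothesis is directional, so one-sided 0.05 is tried first.

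- Pass rule: the largest c with P(X ≤ c | 120, 0.25) ≤ 0.05.
- P(X ≤ 21)=0.0330 and P(X ≤ 22)=0.0534, so the trial passes with 21 events or fewer.
- Power: P(X ≤ 21 | 120, 0.145)=0.8556, which matches the stated 85.6%. One-sided 0.025 gives 79.3%, so one-sided 0.05 is the plan's test.

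**3. How many cases change a boundary result**

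- *Replacement, n held at 120.* A true tally of 22/120 (p=0.053, fail) becomes 21/120 (p=0.033, pass) if one failure is left out and an event-free patient takes its place.
- *Restoration, n allowed to grow.* Adding k omitted failures to an observed 21/120:
  - k=1: 22/121, p=0.048, still passes
  - k=2: 23/122, p=0.069, fails
  - k=3: 24/123, p=0.094, fails

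**4. False-pass probability**

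Suppose the true rate among all attempted cases is exactly 25%, and m of every 120 attempted cases are failures that go unenrolled and are replaced. With d=m/120, the rate among those enrolled is q=(0.25−d)/(1−d), and the chance of passing is P(X ≤ 21 | 120, q).

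| m (assumed) | d | q | Chance of a false pass |
|---|---|---|---|
| 0 | 0 | 0.2500 | 3.3% |
| 1 | 0.0083 | 0.2437 | 4.6% |
| 3 | 0.0250 | 0.2308 | 8.7% |
| 5 | 0.0417 | 0.2174 | 15.5% |

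The documents give no expected number of such failures. The values of m only show how the result moves.

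**The case against.** **The implanted-population rule does most of the work.** Sections 4.1 and 9.3 analyse only subjects who received an implant. A catheter that cannot be introduced leaves no implant, so on that wording the patient is outside the 1-month analysis under any enrolment trigger. This stands, and it means that harmonising the trigger alone does not bring such cases into the endpoint. It does not remove the conflict. Section 7.1 calls the aborted case a technical failure and Section 9.2 analyses all 120. A patient with a Verta stent already deployed could also count as implanted yet be unenrolled under Section 8.3.

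**Screen-failure status is inferred.** A reader might take Section 5.3 to make these patients screen failures. It does not say so. It places screen failure within the screening process, which Sections 1.2 and 8.1 describe as site, Core Lab and Case Review Board review. What it does say is that they are not enrolled.

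**One case need not change the result.** A reader might infer that any single reclassified failure flips the trial. The arithmetic does not support that. Adding one omitted failure to 21/120 still passes; a one-case flip needs a tally exactly at the boundary and an event-free replacement patient.

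**Such cases may be rare.** All five published series in Table 3 report 100% technical success, and for a case stopped after Verta insertion only the outlying sentence in Section 8.3 drops the patient. Both points stand and may make the effect small. Against them, Section 4.1 pools roll-in cases by investigators with no ChEVAS experience into the primary analysis.

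**Section 8.4 is not a fourth enrolment trigger.** It concerns adverse-event capture, and starting at operating-room entry makes losing safety events less likely. It still needs aligning, because the same item also says capture begins after enrolment.

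**Other documents may settle it.** The protocol defers population detail to an SAP whose text is not in the public document, and the chimney-first order comes from the background overview, while Section 8.3 defers to an IFU that is not supplied. A resolving rule cannot be excluded, but sites enrol from the protocol.

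**Conclusion.** The inconsistency is real and sits in current text. The same aborted case can be an enrolled technical failure or not enrolled, and the narrower readings move the 1-month rate in one direction, towards passing. How far cannot be known from the documents. The false-pass figures assume a true rate of exactly 25%, that every such failure is left out and replaced, and 1, 3 or 5 cases per 120. At one case the false-pass chance (4.6%) stays below the nominal 5%; only the larger assumed counts exceed it.

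This is not a sample-size error: 120 subjects and 85.6% power both reproduce. Nor would correcting the trigger settle the matter alone, because the implanted-population rule would still exclude an aborted case that has no implant.

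**What to change.** - **One trigger.** Use the first attempt to insert any ChEVAS System catheter, already the rule in Sections 1.2 and 7.1, in Sections 4.1, 5.3 and 8.3 as well.
- **Close the screening route.** State in Section 5.3 that nobody can be recorded as a screen failure after that point.
- **Align adverse-event capture.** Make the start in Section 8.4 consistent with the trigger, and list separately any patient whose procedure is abandoned after operating-room entry but before it.
- **Reconcile the analysis set in the same edit.** Amend the implanted-population wording in Sections 4.1 and 9.3 to agree with Sections 7.1 and 9.2, so that every enrolled ChEVAS subject is in the 1-month denominator and an aborted case without an implant counts as a technical failure. Carry the same rule into the SAP.

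The cost is a few sentences, settled before outcomes are known. No patients or procedures are added, and the planned 120 subjects and 85.6% power are unchanged. The downside for the sponsor is that the observed 1-month rate may be slightly less favourable.

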8.4 SAFETY AND OTHER ASSESSMENTS

Information collected at the following procedures/evaluations, as applicable:

- **Physical examination** Including weight, blood pressure, medication assessment. If patient exhibits potential neurological change, the patient will undergo an mRS exam for endpoint analysis
- **Blood Laboratory Analysis** Including Serum Creatinine, eGFR (calculated)
- **Contrast-enhanced CT scan:** imaging requirements include slice thickness of $\leq 3\text{mm}$; axial, coronary, sagittal views. To ensure consistency, below are the requirements for CT acquisition:
 - Only high resolution, contrast-enhanced spiral CT scans are acceptable. Sites are required to use radiation reduction techniques
 - Data must be uncompressed
 - **Preferred maximum slice spacing is 2mm.** In no case should it exceed 3mm
 - The preferred protocol, shown below, is easier to attain with a multi-row scanner. If the preferred protocol cannot be used, an alternate protocol is provided.
 - Instruct patient not to move during scan. Do not move table height, position, or field of view during scan. If such movement occurs, repeat scan in its entirety.

Parameter	Preferred	Alternate
Scan Mode	Helical/Spiral	
Scan Parameters	140kVp, Auto mA, 0.5sec	140kVp, 280mA (min), 1.0sec
Collimation	0.625 to 2mm	3mm
Slice Spacing	0.625 to 2mm	3mm
Superior Extent	Cervical Spine – C2 or base of ears	
Inferior Extent	Lesser trochanter of femur	
Patient Instruction	Single breath hold	1 st hold: above celiac to bifurcation 2 nd hold: bifurcation to lesser trochanter
Contrast*	Standard non-ionic	
Volume and Rate	150mL at 3 to 4 mL/sec or as per institutional standards	
Scan Delay	ROI - threshold 90Hu in aorta	
Field of View	Large body	
Window Level	400/40	

*For those subjects with renal insufficiency, a non-contrast CT and duplex ultrasound will be acceptable.

- **Procedural Information:** The Index Procedure CRF will capture all relevant procedural data including access times and types, anesthesia type, all devices implanted, any adjunctive devices used, timing of procedural events, post-procedural findings, complications and concomitant procedures performed, blood loss, contrast volume, fluoroscopy time and any observations on the procedure
- **Adverse Events:** these will be captured at any point after enrollment until study exit. This is determined by the time the patient enters the operating room or catheter lab.
- **Assessment of adverse events.** All reported adverse events will be reviewed and assessed by the Endologix Safety team.

